## 8.7 ADMINISTRATIVE STRUCTURE OF THE TRIAL

The trial is sponsored by Boehringer Ingelheim (BI).

A Coordinating Investigator is responsible to coordinate investigators at the different sites participating in this trial. Tasks and responsibilities are defined in a contract.

A DMC will be established. Members of the DMC are independent of BI, they are physicians experienced in the treatment of the disease under investigation and a statistician.

The DMC will evaluate safety data. While DMC members may be unblinded, measures are in place to ensure the blinding for everyone else involved in the trial. Regular DMC meetings will be held at specified intervals. The DMC will recommend continuation, modification or termination of the trial as detailed in the DMC charter. DMC recommendations as well as the final BI decision will be reported to the appropriate Regulatory Authorities (RAs)/Health Authorities (HAs), IRBs/ECs, and to investigators as requested by local law. The tasks and responsibilities of the DMC are specified in a charter.

Relevant documentation on the participating (Principal) Investigators (e.g. their curricula vitae) will be filed in the ISF.

The investigators will have access to the BI web portal Clinergize to access documents provided by the sponsor.

BI has appointed a Clinical Trial Leader (CT Leader), responsible for coordinating all required activities, in order to

- manage the trial in accordance with applicable regulations and internal SOPs,
- direct the clinical trial team in the preparation, conduct, and reporting of the trial,
- ensure appropriate training and information of Clinical Trial Managers (CT Managers), Clinical Research Associates (CRAs), and investigators of participating countries.

The organisation of the trial in the participating countries will be performed by the respective local or regional BI-organisation (Operating Unit, OPU) in accordance with applicable regulations and BI SOPs, or by a Contract Research Organisation (CRO) with which the responsibilities and tasks will have been agreed and a written contract filed before initiation of the clinical trial.

Data Management and Statistical Evaluation will be done by BI according to BI SOPs.

Tasks and functions assigned in order to organise, manage, and evaluate the trial are defined according to BI SOPs. A list of responsible persons and relevant local information can be found in the ISF.

A central laboratory service, a central service evaluating ECG, a vendor for cognitive and neuropsychological assessments, a vendor for medication adherence monitoring, a vendor for duplication checks, a vendor for speech sample analysis and an IRT vendor will be used in this trial. Details will be provided in the respective manuals, available in the ISF.

## **10. APPENDICES**

### **10.1 TIME SCHEDULE FOR PHARMACOKINETIC (PK) BLOOD SAMPLING**

Table 10.1: 1 Time schedule for PK blood sampling

| Visit | Day | Time Point                                       | CRF Time/
PTM | Event |
|--------------|------------|---|--------------------------|--------------|
| 3            | 22         | Preferrably within 30 min
before drug administration | ~0:30                    | PK Blood     |
| 4            | 43         |   |                          |              |
| 6            | 85         |   |                          |              |
| 8            | 127        |   |                          |              |
| EoT          | 183        | ~1 day after last dose                                  | ~24:00*                  |              |
| (e) EOT      | NA         | ~as applicable after last dose                          | ~24:00*                  |              |

\*PK sample should be collected within the visit window. Precise collection timepoint must be captured in the eCRF.

## **10.2 DEFINITION OF STUDY PARTNER AND CAREGIVER**

| Who can be a study partner?   | Who can be a Caregiver?  |
|--|---|
| Study partner is any person who knows the patient well, has been capable of interacting with the patient on regular basis, preferably consistent throughout the study, either private or professional    | Caregiver is a study partner who is taking informal (unpaid) care of the patient, which can be direct or indirect, including e.g. organizing or checking things for the patient, making phone calls, managing bills, arranging things and doing paperwork related to the patient, do shopping, cooking, cleaning, laundry, etc. |
| Every patient enrolled in the study must have a study partner  | Patients do not need to have a caregiver but must have a study partner. Therefore, having a caregiver is optional.  |
| Must sign study partner IC   | Will be asked to complete additional questionnaires (SCQ, EQ-5D-5L) for caregiver assessment consent on study partner IC  |
| The study partner must interact with the patient minimum 1 hour per week and, preferably, at least 2 times a week. At least one interaction per week should be in person.                                | As caregiver, study partner should spend an average of approximately 4 hours per week or more with care giving (direct or indirect, see above).   |
| Don't need to be co-resident with the patients.  |   |
| Must have educational achievement of minimum 8 th grade.  |   |
| Professional study partner (e.g. study nurse, social worker etc.) are allowed if not involved in administration of any of the protocol assessments.  | Professional study partners cannot be caregiver as they are providing paid care.  |
| Will provide input to SCoRS, PANSS, SPGI-S, SPGI-C.

Study partners who are NOT caregivers, will not complete, EQ-5D-5L and SCQ to assess caregiver's Quality of life and the burden of caregiving | In addition to SCoRS, PANSS, SPGI-S, SPGI-C, the care-giver will complete EQ-5D-5L and SCQ to assess caregiver's Quality of life and the burden of caregiving.  |

## **10.3 POTENTIAL MODIFICATION OF TRIAL CONDUCT IN CASE OF RESTRICTIONS DUE TO COVID-19 OR OTHER EXCEPTIONAL CIRCUMSTANCES**

In case of any restrictions during the COVID-19 pandemic or any other exceptional circumstances (e.g. emergency, natural disaster, patient specific situations, etc.) study conduct may need to be adjusted based on the investigator's discretion and agreed with the sponsor.

Local regulatory and legal requirements of the participating country need to be respected for all modifications. Patients need to be informed about the modifications and agree to them before implementation.

If on-site / clinic visits are not possible because the site/institution is limiting or restricting on-site visits due to COVID-19 (or any other exceptional circumstances), some of the visit procedures (including study partner contacts and assessments) can be done via home visit or telephone / video conference or locally (e.g. at a local lab, diagnostic centre, GP visit, etc.).

All COVID-19/exceptional circumstances-related deviations from the original schedule of visits and procedures will be documented, and the implications will be considered for the analysis of trial data.

The following contingency measures will be introduced to ensure patient safety and appropriate trial continuation based on a thorough benefit-risk assessment of treatment continuation versus early discontinuation, to be judged by the investigator on an individual patient level whereby patient safety always needs to be at the centre of decision-making (see [Section 1.4](#)).

The following study data should be collected/ reported during home and/or remote visit and/ or obtained locally:

- Birth control check (for women of childbearing potential)
- Safety and pregnancy test
- Vital Signs
- ECG
- Adverse Events
- Concomitant Therapies
- All scheduled scales and questionnaires (if possible)
- Study medication compliance check

### **Birth control check (for women of childbearing potential)/ pregnancy test**

- The Investigator or designee must confirm with the patient (and study partner, if possible) that a reliable birth control method is being used consistently.
- Women of childbearing potential should have a pregnancy test performed if indicated in the [Flow Chart](#) or is required based on local regulations or investigator discretion.

### Safety assessments:

- If home visits are possible, some assessments can be done at the patient's home (e.g. blood and urine samples, including PK samples, if applicable, can be collected and sent to the central lab, vital signs).
- If blood sampling or analysis by the central lab is not possible, safety lab analyses can be performed at a local laboratory. The results of the lab tests must be reported to the investigator who ensures medical review and proper documentation in the eCRF.
- At a minimum the haematology panels should be done. Other safety laboratory tests may be performed at the Investigator's discretion.
- For the rare situations in which the safety laboratory test cannot be done, the investigator's reasoning and decision-making process must be documented in source notes at the site.

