#### 4.1.5 Blinding and procedures for unblinding

##### 4.1.5.1 Blinding

Except for independent DMC, patients, investigators, central reviewers, and everyone involved in trial conduct or analysis or with any other interest in this double-blind trial will remain blinded with regards to the randomised treatment assignments until the database is declared ready for analysis according to the sponsor's SOPs. Further details regarding the timepoint of unblinding the database for analysis are documented in the TSAP.

The access to the randomisation code will be kept restricted until its release for analysis.

Long-term treatment with GLYT1 inhibitors such as Iclepertin may reduce Hb levels in some patients. Phase II results from the 1346-0009 trial showed that the majority of patients (over 90%) have Hb levels that remain in the normal range ([c31477880](#) table 15.3.2.2.). It is also noted that decreases in Hb have also been observed in some placebo patients, as there can be considerable fluctuation in Hb values. The number of patients with decreased Hb, by at least >2 g/dl, was the same in placebo group, as in the active treatment arms ([c31477880](#)). Therefore, reductions in Hb may not permit investigators to infer which treatment arm individual patients had been allocated to.

Nonetheless, in order to ensure the double-blind nature of the trial, the Hb related parameters will be blinded to the investigator and sponsor starting at visit 2 until the end of trial. The site will receive alerts as detailed in [Section 5.2.6.4](#). The Hb related parameters will be reviewed throughout the trial by an independent, third party as well as by the independent DMC. For medical management of any patient with an alert on decreased Hb, refer to Section 5.2.6.4.

The responsible bioanalyst of the external bioanalytical laboratory will receive the randomization codes prior to last patient completed to allow for the exclusion from the analyses of pharmacokinetic (PK) samples taken from placebo patients.

The trial bioanalyst (TBA) may receive unblinding data from external bioanalytical laboratory after the last patient completed the last visit but prior to official unblinding of the trial database for preparation of data transfer (e.g. check file structure prior to data upload and SDTM transformation and bioanalytical report writing).

Bioanalytics will not disclose the randomisation code or the results of their measurements until the trial is officially unblended.

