### **5.2.3 Safety laboratory parameters**

Safety laboratory parameters to be assessed are listed in [Table 5.2.3: 1](#). For the sampling time points please see the Flow Chart.

Patients do not have to be fasted for the blood sampling for the safety laboratory. All analyses will be performed by a central laboratory, the respective reference ranges will be provided in the lab manual in the ISF.

Instructions regarding sample collection, sample handling/ processing and sample shipping are provided in the Laboratory Manual in the ISF.

The central laboratory will send reports to the investigator (except for blinded Hb related parameters, for further details refer to [Section 4.1.5.1](#) and [Section 5.2.6.4](#)). Laboratory values that are out of range should be commented on lab report printouts and evaluated by the investigator for clinical significance.

Clinically significant abnormal laboratory results should be reported by the investigators in the eCRF either on baseline condition (from Visit 1 test) or on AE page (from subsequent visits test). Please refer to [Section 5.2.6](#).

Clinically relevant abnormal laboratory test results will need to be followed per investigators judgment, until normalization or stabilization or until an alternative explanation has been found.

Safety lab may be repeated for any or all lab parameters specified in the protocol, at any time point during the study, per investigators discretion.

In case the criteria for hepatic injury are fulfilled, a number of additional measures will be performed (please see [Section 5.2.6.1](#) and the DILI Checklist provided in the eDC system.) The amount of blood taken from the patient concerned will be increased due to this additional sampling.

The central laboratory will transfer the results of the analysis to the sponsor.

The site should not use a local laboratory to assess the Haematology parameters unless clinically justified.

Table 5.2.3:1

Safety laboratory tests

| Category  | Test name  |  |
|---|--|--|
| Haematology Panel A
(Refer Section 5.2.6.4 )  | Haemoglobin (Hb)
Haematocrit (Hct)
MCV, MCH, MCHC
RDW   | Red Blood Cell Count/ Erythrocytes
Reticulocyte Count
Reticulocyte index   |

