#### 5.2.6.4 Haemoglobin and Anaemia

To reduce bias on efficacy assessments, starting at visit 2 until the end of trial, **Haematology Panel A parameters** (refer [table 5.2.3:1](#)) will be blinded to the site and to the sponsor.

Sites will be alerted if the following occurs:

- **Alert 1:** Hb decrease > 20 g/L (2 g/dL) compared to baseline value
- **Alert 2:** The Hb value is **below** the normal reference range
- **Alert 3:** Hb value fulfils the criteria to withdraw the treatment (refer to [Section 3.3.4](#))

An independent third party will review both **haematology panels** parameters throughout the trial. In addition, the independent DMC will review unblinded safety data on a regular basis throughout the study.

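### Patients tested at a local laboratory fall outside the haemoglobin blind: Appendix 10.3 sends their Haematology Panel A values to the investigator and the eCRF, with no route to the independent reviewer and no alert step

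*Protocol*

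**What the plan says.** **The blind.** Protocol Section 4.1.5.1 states that "the Hb related parameters will be blinded to the investigator and sponsor starting at visit 2 until the end of trial". Section 5.2.6.4 applies this to all of Haematology Panel A, which "will be blinded to the site and to the sponsor", and gives the purpose: "To reduce bias on efficacy assessments, starting at visit 2 until the end of trial". Table 5.2.3:1 places Hb, haematocrit, red cell indices and reticulocytes in Panel A.

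**Normal conduct.** Under Section 5.2.3 the central laboratory reports to the investigator "except for blinded Hb related parameters". Under Section 5.2.6.4 the site learns only whether Alert 1, 2 or 3 has been triggered. An independent third party reviews both haematology panels, and the DMC reviews unblinded safety data.

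**Local testing.** Section 5.2.3 discourages it but leaves an exception: "The site should not use a local laboratory to assess the Haematology parameters unless clinically justified". Appendix 10.3 (Safety assessments) permits local analysis when central sampling or analysis is not possible. On content it says "At a minimum the haematology panels should be done", and on routing "The results of the lab tests must be reported to the investigator who ensures medical review and proper documentation in the eCRF".

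Appendix 10.3 does not refer back to Section 4.1.5.1 or 5.2.6.4. Nothing in the SAP text available restricts access to locally measured Hb.

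**The concern.** An investigator who follows Appendix 10.3 sees the Hb value that two other sections withhold. An investigator who respects those sections cannot comply with the appendix. The appendix covers COVID-19 restrictions and other exceptional circumstances, including situations specific to one patient, so it is not tied to the pandemic alone.

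Two things are at stake.

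- **Rating bias.** SCoRS is a key secondary endpoint and is rater-judged, as are the CGI scales. Section 6.2.1 keeps SCoRS raters unaware of MCCB and VRFCAT performance but says nothing about laboratory values. Section 5.1 allows the CGI-S rater to be the investigator, who is the person Appendix 10.3 names as recipient.
- **The alert pathway.** Alert 1 and one limb of the withdrawal criterion in Section 3.3.4.2 compare Hb with baseline. Section 7.2.1 defines baseline in general as the pre-dose Visit 2 value, which is blinded to the site. On the text, the site holds the local value without that baseline, and the third party is not sent the local value.

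**Working it through.** The protocol gives no figure on this point to reproduce, so the check is a comparison of texts, followed by a side calculation of how informative one Hb value is.

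**Step 1: the same parameters, two instructions.**

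| Question | Sections 4.1.5.1, 5.2.3, 5.2.6.4 | Appendix 10.3 |
|---|---|---|
| Which tests? | All of Panel A | Haematology panels (plural), so Panel A is included |
| Who sees the values? | Third party and DMC; not site or sponsor | Investigator, and the eCRF |
| Any exception for Panel A? | Omitted from central laboratory reports | None stated |
| Who generates alerts? | Site is alerted to Alerts 1 to 3; third party reviews both panels | Not stated |

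**Step 2: who is affected.** The local route opens only when central sampling or analysis is not possible. Appendix 10.3 also allows samples taken at home to be sent to the central laboratory, and those stay blinded. The affected group is therefore the patients and visits using a local laboratory under Appendix 10.3, plus any local haematology under the Section 5.2.3 exception. For the latter, no recipient or masking step is stated. The documents do not say how often either will occur.

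**Step 3: investigator and sponsor.** Disclosure to the investigator is explicit. Disclosure to the sponsor is inferred: the value is entered in the eCRF, and Section 8.7 says the sponsor does data management. A restricted eCRF page is possible but is not described.

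**Step 4: how much one value reveals.**

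- Phase II mean Hb change (Table 1.4.2:1): -3.3 g/L on 10 mg and -0.5 g/L on placebo.
- Gap: 3.3 - 0.5 = 2.8 g/L.
- SD of the change: not in the documents. Assumed 7 to 10 g/L, with 6 and 12 shown as wider limits.
- Model: normal distributions with equal SD, 1:1 allocation. The best guess cuts halfway between the means and is correct with probability Phi(2.8 / (2 x SD)).

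| Assumed SD (g/L) | 2.8 / (2 x SD) | Probability of a correct guess |
|---|---|---|
| 6 | 0.233 | 0.592 |
| 7 | 0.200 | 0.579 |
| 8 | 0.175 | 0.569 |
| 10 | 0.140 | 0.556 |
| 12 | 0.117 | 0.546 |

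Chance is 0.50. One value improves the guess by about 6 to 8 percentage points over the assumed range of 7 to 10 g/L. Repeated local values could add to this; differences between laboratories could take away from it. Neither is modelled.

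**The case against.** The strongest reply is that this is a narrow safety fallback. Changes under Appendix 10.3 must be agreed with the sponsor, and the deviations are documented and considered in the analysis. Section 5.2.3 shows that the authors had thought about local haematology and accepted an exception on clinical grounds. Section 4.1.5.1 reports that Hb falls of more than 2 g/dL were as common on placebo as on active treatment in phase II, and that Hb reductions may not reveal the arm. Sites already receive alerts, so the leak is only the information beyond them. MCCB and VRFCAT are performance tests and are less open to a rater's expectation.

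Most of this stands, and it limits the point in four places where a reader might infer more:

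- **That the Hb blind as a whole is undone.** The documents do not support this. It fails only where local testing is used.
- **That Hb identifies the arm.** Both the protocol's own account and the calculation say it does so only weakly. The chance of ranking an active patient below a placebo patient, Phi(2.8 / (SD x sqrt 2)), is 0.61 to 0.58 for SD 7 to 10. That describes a comparison of two patients, whereas a site sees one patient at a time.
- **That the sponsor will see the values.** This depends on eCRF access rules that the documents do not give.
- **That a guessed arm would change the primary analysis through the call on drug-relatedness.** Withdrawal for Hb decrease is a treatment-policy event in its own right (Protocol Section 7; SAP Table 6.3:1), so those data stay in whatever the relatedness call. An effect on relatedness calls for other events is speculative.

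What the objection does not remove is the conflict itself. Having given its reasons why Hb may not be revealing, Section 4.1.5.1 still imposes the blind. The appendix should either respect it or state the exception and its safeguards. The missing alert step is also not answered by saying that Hb is uninformative.

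**Conclusion.** The point holds for patients tested locally. Appendix 10.3 contradicts Sections 4.1.5.1 and 5.2.6.4 on who may see Panel A. It also leaves local values with no route to the independent reviewer and no alert step. Section 5.2.3 leaves a similar gap through its exception. The passages must be reconciled.

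The likely effect on the efficacy results is small unless local testing is frequent, and the documents give no frequency. The 56% to 58% figure rests on the phase II means, an assumed SD of 7 to 10 g/L and a normal model for a single value. Confidence is high for disclosure to the investigator and for the absence of a stated alert route, and lower for disclosure to the sponsor. No sample size, power or alpha figure is affected.

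**What to change.** Amend Appendix 10.3 and Section 5.2.3, with a matching laboratory-manual instruction, to say that for locally measured Panel A values:

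1. The result goes to the independent third party named in Sections 4.1.5.1 and 5.2.6.4, so that the existing alerts can be generated against the blinded baseline.
2. The result is entered on an access-restricted eCRF page that the blinded sponsor team cannot see.
3. Where someone at the site must see the value for patient safety, it is kept from those who rate SCoRS and CGI and those who administer MCCB and VRFCAT for that patient.
4. The patient is flagged among the deviations already documented under Appendix 10.3, and cases under the Section 5.2.3 exception are flagged in the same way.

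This concerns only data access and routing. Alert thresholds, safety testing and clinical actions are unchanged.

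The cost is protocol and manual wording, some handling effort, and setting up a data route that the documents do not yet describe. They do not show that the third party can already receive local reports from about 100 centres, so that needs to be confirmed. The route should be set up so that it does not delay safety information.

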### ECG:

- The ECG assessment can be done locally. The ECG report must be transferred to the investigator who ensures medical review and proper documentation in the eCRF.
- In rare situations in which the ECG(s) cannot be done, (even locally) and if ECG is normal or does not have any clinically significant findings at prior visits (per investigator's clinical judgment), the Investigator needs to consider the overall patient medical status, including premorbid conditions, before allowing the patient to continue on study treatment.
- In case ECG(s) cannot be done but the patients will be permitted to continue in the study and continue receiving the investigational product, this should be documented in the source documentation.

